Title: Stress, Sex, and Fear

NCT number: 03786952

Document date: 10/7/2019

Study protocol

Participants reported to the PI's laboratory for 1-hr sessions on two consecutive days. On Day 1, informed consent was obtained from participants, after which they completed a short demographics (i.e., age, sex, ethnicity) questionnaire. Participants were then randomly assigned to experience acute stress (socially-evaluated cold pressor test; SECPT) or a control manipulation. Participants assigned to the acute stress condition placed their dominant hand in ice cold (0-2 degrees Celsius) water for up to 3 min. They were also misleadingly informed that they were being videotaped for the analysis of facial expressions and were asked to stare at a camera throughout the manipulation (social evaluative component). Participants assigned to the control condition placed their dominant hand in lukewarm (35-37 degrees Celsius) water for up to 3 min. The water was maintained at the appropriate temperature by a circulating water bath. Participants rated, at 1-min intervals, the painfulness and stressfulness of the stress or control manipulation on scales of 0-10 (0 = lack of pain/stress; 10 = unbearable pain/stress).

Immediately or 30 min later (determined via random assignment), participants underwent a fear-potentiated startle paradigm, in which differential fear conditioning was employed. The conditioned stimuli (CSs) and generalization stimuli (GSs) consisted of nine black circles of increasing diameter, which were presented on a white background of a computer monitor (via SuperLab software; Cedrus Corporation, San Pedro, CA, USA). The monitor was located approximately 124 cm in front of participants. The smallest circle was 8.5 mm in diameter, and each larger circle increased in size by 2.5 mm, ending with the largest circle, which was 29 mm in diameter. For approximately half of the participants, the smallest circle served as the CS+, and the largest circle served as the CS-. For the remaining participants, the largest circle served as the CS+, and the smallest circle served as the CS-. The circles sized between the CS+ and the CS- were the GSs and were only presented to participants on Day 2. The unconditioned stimulus (US) was a 250-ms, 140-p.s.i. airblast aimed at the larynx. The startle probe was a 40-ms, 108-dB burst of white noise that was delivered to participants through a pair of headphones. During CS+ trials on Day 1, the startle probe was presented 6 s after onset of the CS, which was followed 500 ms later by presentation of the US; the CS+ terminated 500 ms after the onset of the US. During all GS and CS- trials (and CS+ trials on Day 2), the startle probe was presented 6 s following the onset of the stimulus, without any presentation of the US; stimulus presentation ended 250 ms after the startle probe. On noise alone (NA) trials, only the startle probe was presented while participants looked at the white background on the computer monitor; the length of NA trials matched the length of the startle probe (i.e., 40 ms).

Fear acquisition on Day 1 began with three NA trials, followed by a habituation phase that included four NA, CS+, and CS- trials. The CS presentations during habituation were not followed by the US. After habituation, participants underwent the conditioning phase, which included three blocks of four trials of each stimulus type (NA, CS+, CS-); this resulted in 12 trials per block and 36 total trials. During conditioning, the CS+ was always paired with the US (i.e., 100% reinforcement rate). On Day 2, participants completed the generalization phase of the paradigm. This phase began with three NA trials, followed by three blocks of one trial of each stimulus type (NA, CS+, seven GSs, CS-) for a total of 10 trials per block and 30 total trials. No CS or GS presentation during the generalization phase was reinforced with the US. Fixed trial orders were used for all participants. The only restrictions were that, during acquisition, there were 4 trials of each trial type (i.e., NA, CS+, CS-) for each block of 12 trials and, during generalization, there was 1 trial of each trial type (i.e., NA, CS+, seven GSs, CS-) for each block of 10 trials. The fixed trial order involved randomizing the trial types within each block. The intertrial interval was random, between 9 and 22 s in duration.

Electromyographic (EMG) recordings of the right orbicularis oculi muscle were used to measure participants' startle responses. Ag/AgCl electrodes (5-mm) that were filled with electrolyte gel were placed 1 cm below the pupil of the right eye, 1 cm below the lateral canthus, and over the mastoid behind the right ear (ground). The impedance levels for each participant were less than 6 kΩ. Electrodermal activity (EDA) was measured by placing Ag/AgCl electrodes on the hypothenar surface of the hand. EMG and EDA activity were sampled at 1000 Hz and amplified and digitized with the appropriate Biopac modules of the Biopac MP150 system (Biopac Systems, Inc., Aero Camino, CA, USA) and its accompanying Acqknowledge data acquisition and analysis software (Biopac Systems, Inc., Aero Camino, CA, USA). The Acqknowledge data files were imported into the MindWare EMG or EDA analysis program (MindWare Technologies, Ltd., Gahanna, OH, USA). This program was used to filter and smooth the EMG and EDA signals. The EMG signal was amplified with a gain of 2000; it was filtered with low and high-frequency cutoffs at 28 and 500 Hz, respectively, and a 60-Hz notch filter was applied. The peak EMG signal 20–200 ms after each startle probe was used as a measure of the startle response. Skin conductance responses to the CSs and GSs were quantified by calculating the average increase (from a 1 s pre-stimulus baseline) 3-6 s after stimulus onset.

Participants used a three-button response keypad (SuperLab software, Cedrus Corporation, San Pedro, CA, USA) to report their expectation of the US during each CS+, GS, and CS- trial on Days 1 and 2. When each stimulus was presented on the computer monitor, participants pressed an “AIR” key if they expected the US to occur, a “NO AIR” key if they did not expect the US to occur, and a “?” key if they were unsure if the US would occur. For data analysis, “AIR” responses were scored as +1, “?” responses were scored as 0, and “NO AIR” responses were scored as -1.

Participants’ heart rate was measured for 1 min prior to and continuously throughout the stress or control manipulation via the PPG module of the Biopac MP150 system.

Saliva samples were collected at several time points on Day 1 (4 samples) and Day 2 (2 samples) to measure salivary hormones [cortisol, alpha-amylase, estradiol (in females), progesterone (in females)]. Saliva samples were collected via the SalivaBio Oral Swab (Salimetrics LLC, State College, PA). The samples stored at -20°C until assayed in duplicate by enzyme immunoassays (EIAs) (Salimetrics LLC). Saliva samples 1 (baseline) and 4 (25 min post-stress) from Day 1 were assayed for cortisol to assess stress-induced changes in hypothalamus-pituitary-adrenal axis activity. Saliva samples 1 (baseline) and 2 (post-generalization test) from Day 2 were assayed for cortisol to control for the influence of salivary cortisol levels on generalization testing. Saliva samples 1 (baseline), 2 (middle, or 1.5 min mark, of stress or control manipulation), and 3 (immediately following stress or control manipulation) from Day 1 were assayed for alpha-amylase to assess rapid stress-induced changes in sympathetic nervous system activity. Saliva samples 1 and 4 (from females) from Day 1 and saliva sample 1 (from females) from Day 2 were assayed for progesterone. The first saliva samples (from females) from Days 1 and 2 were assayed for estradiol.

Following the completion of generalization testing on Day 2, participants completed the Spielberger State-Trait Anxiety Inventory (STAI-Trait) to quantify participants’ state and trait anxiety levels, the Anxiety Sensitivity Index (ASI) to assess participants’ anxiety sensitivities, the PTSD Checklist – Civilian Version to examine symptoms of post-traumatic stress disorder, the Center for Epidemiological Studies Depression Scale (CES-D) to measure symptoms of depression, and the Childhood Trauma Questionnaire (CTQ) to quantify childhood abuse and neglect.

Statistical analyses

To assess time-dependent changes in subjective and objective stress response measures, we performed separate mixed-model ANOVAs on each of the following measures: Day 1 cortisol levels, Day 2 cortisol levels, alpha-amylase levels, heart rate, subjective pain ratings, and subjective stress ratings. Stress, stress time point, and sex were entered as categorical, between-subjects factors. Time point of measurement for each measure was entered as the within-subjects factor in each analysis.

EMG difference scores, skin conductance responses, and US expectancy ratings from acquisition (Day 1) and generalization testing (Day 2) were subjected to separate mixed-model ANOVAs with stress, stress time point, and sex entered as categorical, between-subjects factors. Trial block (4 for acquisition; 3 for generalization) and trial type (acquisition: CS+, CS-; generalization testing: CS+, CS-, 4 generalization stimuli) were entered as within-subjects factors in these analyses.

For all statistical analyses, alpha was set at 0.05. In the case of post hoc testing, alpha was adjusted with Bonferroni corrections so that the family-wise error rate did not exceed 0.05.

A priori power analyses were performed with G*Power 3.1.9.2 (University of Kiel, Germany). The power analyses revealed that we would need approximately 565 participants to retain adequate statistical power ($1-\beta = 0.8$) to detect small-to-moderate effect sizes ($f = 0.145$) for main and interactive effects of all independent variables outlined above.

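### Minor: which circle served as CS+ is in none of the six fear ANOVAs, which may cost precision and is cheap to mend; Day 2 cortisol, assayed as a control, is in no generalization model

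*Combined protocol and SAP*

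**What the plan says.** All references are to the combined protocol and SAP.

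**Circle assignment.** Under "Study protocol", the description of the stimuli states: "For approximately half of the participants, the smallest circle served as the CS+, and the largest circle served as the CS" (the quoted run stops just before the minus sign). The remaining participants had the reverse. How participants were allotted to the two versions is not stated. For the other two manipulated factors it is: "Participants were then randomly assigned to experience acute stress" for stress, and "Immediately or 30 min later (determined via random assignment" for the interval before conditioning.

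**Fear models.** Under "Statistical analyses", three measures (EMG difference scores, skin conductance, US expectancy) in two phases are analysed in "separate mixed-model ANOVAs with stress, stress time point, and sex entered as categorical, between-subjects factors". The within-subjects factors are given as "Trial block (4 for acquisition; 3 for generalization) and trial type", with two trial types at acquisition and six at generalization. No other factor and no covariate is listed.

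**Cortisol.** The two Day 2 saliva samples "were assayed for cortisol to control for the influence of salivary cortisol levels on generalization testing". The analysis section uses Day 2 cortisol once, as one of the outcomes in the list "Day 1 cortisol levels, Day 2 cortisol levels, alpha-amylase levels, heart rate, subjective pain ratings, and subjective stress ratings".

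**Size.** The power statement is that "we would need approximately 565 participants to retain adequate statistical power" of 0.8 at f = 0.145.

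**The concern.** Suppose the larger circle draws a larger (or smaller) response whatever its role. Then CS+ minus CS- is shifted one way in participants whose CS+ was the largest circle, and the other way in the rest. Counterbalancing makes these shifts cancel on average. It does not remove the spread that they create between participants. A model without the factor leaves that spread in the error of the trial-type and stress-by-trial-type tests, which are the tests of whether stress alters discrimination and generalization. If circle size has no effect, nothing is lost.

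Because the allotment is not described, a reader also cannot check whether the two versions were spread evenly over the eight stress x time point x sex cells.

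The cortisol point is separate and smaller. A purpose is stated for the Day 2 assay that no listed model carries out.

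**Working it through.** **Count of models.** 3 measures x 2 phases = 6. None contains circle assignment. The 3 generalization models contain no cortisol term.

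**The plan's own figure.** The 565 cannot be reproduced, because the numerator df, number of groups and correlation used are not given. For a fixed-effects ANOVA with 8 cells, f = 0.145, alpha 0.05 and power 0.80, N is 376 at 1 df, 573 at 4 df and 616 at 5 df. I therefore take 565 as given; the point does not depend on it.

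**Inputs.** N = 565, f = 0.145 and alpha = 0.05 are from "Statistical analyses". Assumptions: circle size shifts a participant's CS+ minus CS- by +d or -d, where d is in SDs of that difference after size is removed (so the halves differ by 2d); the split is even; the test is the 1-df stress-by-trial-type contrast on the difference score, with f relative to an SD of that score.

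**Formula.** Leaving the factor out multiplies the error variance by 1 + d². The baseline noncentrality is 565 x 0.145² = 11.88. Error df are 565 - 8 = 557 without the factor and 556 with it. The documents do not say which SD f refers to, so both readings are shown.

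- Reading A: f is relative to the SD after size is removed. Noncentrality is 11.88/(1 + d²) without the factor and 11.88 with it.
- Reading B: f is relative to the error of the planned model. Noncentrality is 11.88 without the factor and 11.88 x (1 + d²) with it.

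| d | 1 + d² | A: without | A: with | B: without | B: with |
|---|---|---|---|---|---|
| 0 | 1.00 | 0.931 | 0.931 | 0.931 | 0.931 |
| 0.3 | 1.09 | 0.909 | 0.931 | 0.931 | 0.949 |
| 0.5 | 1.25 | 0.868 | 0.931 | 0.931 | 0.970 |
| 0.7 | 1.49 | 0.805 | 0.931 | 0.931 | 0.987 |

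On reading A the omission is equivalent to shrinking the sample to 565/(1 + d²) = 518, 452 and 379 at d = 0.3, 0.5 and 0.7. At d = 0.1 and 0.2, power without the factor is 0.928 and 0.921.

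**Bias.** If assignment was random, chance differences in the split are already counted in the error. Simulated type I error without the factor is 0.051, 0.050 and 0.050 at d = 0.3, 0.5 and 0.7 (20,000 replicates). The chance difference in share between stress and control has SD √(0.25 x 4/565) = 0.042, so 95% lie within 8.2 percentage points. A systematic difference would bias the contrast by 2d x (difference in share). Taking 10 points purely as an illustration, the shift in SE units is 2d x 0.10 / [2√(1 + d²)/√565] = 0.68, 1.06 and 1.36, and type I error is about 0.105, 0.186 and 0.276 at the same three values of d. Both ingredients, a size effect and a systematic imbalance, are hypothetical.

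**Cost in error df (565 complete cases).** Between-subjects 557 to 556. Acquisition: trial type 557 to 556; block and trial type by block 1671 to 1668 each. Generalization: block 1114 to 1112; trial type 2785 to 2780; trial type by block 5570 to 5560.

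**Cortisol.** The stated purpose is control; the only stated use is as an outcome. Modelling cortisol as an outcome can show whether groups differ in it, but it adjusts nothing in the generalization results. No magnitude can be given. A covariate that is constant within a participant and enters only as a main effect would leave the trial-type contrasts unchanged in complete data, so an adjustment needs its interactions with the within-subjects factors.

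**The case against.** The case for leaving the plan alone is a fair one. Counterbalancing already takes an additive size effect out of the average CS+ minus CS-. Every participant sees both circles, so tests on responses averaged over the two are untouched. Pooling over a counterbalanced factor is a legitimate choice. The consequences are modest: on reading A even d = 0.7, a gap of 1.4 SDs between halves, leaves the 1-df test just above 0.80. On reading B no planned power is lost; a gain is forgone. The effects in the power statement are those of the listed variables, which favours reading B without settling it. All of this stands, and it keeps the point minor. It does not answer the precision argument, since balance removes bias but not variance.

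Two limits on the remedy also stand. A factor not crossed with stress, time point or sex adjusts for an additive size effect only. It also adds four terms per model, 24 over the six, which should not become extra hypotheses. And because the analyses are written in the past tense, added terms may be post hoc and should be labelled so if they are.

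A reader might go further and infer that the stress effects are confounded with circle size. The documents do not support that: silence on the method is not evidence of non-random assignment, and nothing suggests that size affects responses.

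On cortisol, the stated purpose may simply mean checking that groups do not differ. The plan does not say so, but rewording it that way would resolve the mismatch.

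**Conclusion.** The point holds as a minor, inexpensive improvement. Circle assignment is a known design factor missing from all six fear ANOVAs. If circle size affects CS+ minus CS-, the trial-type and stress-by-trial-type tests are less precise than the same data allow. For d = 0.3 to 0.7 the difference in 1-df power is 0.02 to 0.13 on reading A (0.931 - 0.909; 0.931 - 0.805) and 0.02 to 0.06 on reading B (0.949 - 0.931; 0.987 - 0.931). These rest on assumed values of d, an even split and f taken on the difference score; at d = 0 the difference is nil.

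It does not follow that the study is underpowered because of this omission, or that its stress contrasts are biased. Bias would require imbalance across cells as well as a size effect, and neither is shown.

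The cortisol mismatch is secondary, is evident from the text alone and has no calculable size. It does not invalidate the unadjusted generalization results. Cortisol on Day 2 is measured after randomisation, so adjusting for it could remove part of a stress effect.

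**What to change.** **Circle assignment.** Add to "Statistical analyses": *Each of the six fear ANOVAs includes CS+ assignment (smallest or largest circle) as a between-subjects factor, with its interactions with block, trial type, and trial type by block. It is not crossed with stress, stress time point or sex. These four terms are nuisance terms and are not tested as hypotheses.* State how assignment was made and report its counts in the eight stress x time point x sex cells. If the analyses have already been run, show the amended model beside the planned one and label it as added later.

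The cost is one between-subjects df, the slightly smaller within-subjects error df listed above, one sentence and a table of counts. Crossing the factor fully would make 16 cells and double the number of effects, which is why it is not proposed; the price is that only an additive size effect is adjusted for.

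**Cortisol.** Choose one of two.

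- Keep the unadjusted generalization ANOVAs as the main analysis and add, as a sensitivity analysis, the same models with centred cortisol from Day 2 sample 1 (before the test) and its interactions with block, trial type, and trial type by block. Sample 2 follows the test and should not be used. This adds three analyses and loses anyone without a sample 1 value.
- Or reword the purpose of the assay as a check for group differences, which costs one phrase.

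### Day 1 cortisol: using the baseline sample as a covariate would usually estimate the stress effect somewhat more precisely than the planned, valid, change test

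*Combined protocol and SAP*

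**What the plan says.** The Study protocol section randomises stress: "Participants were then randomly assigned to experience acute stress (socially-evaluated cold pressor test; SECPT) or a control manipulation". It gives Day 1 cortisol two samples: "Saliva samples 1 (baseline) and 4 (25 min post-stress) from Day 1 were assayed for cortisol". Alpha-amylase has three: "Saliva samples 1 (baseline), 2 (middle, or 1.5 min mark, of stress or control manipulation), and 3 (immediately following stress or control manipulation").

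The Statistical analyses section states its aim for these measures as "To assess time-dependent changes in subjective and objective stress response measures". It then specifies a separate mixed-model ANOVA per measure: "Stress, stress time point, and sex were entered as categorical, between-subjects factors", and "Time point of measurement for each measure was entered as the within-subjects factor in each analysis". No covariate is named. With only two cortisol samples, the baseline has to be one of the two time levels.

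The power statement at the end of that section gives about 565 participants, 80% power and f = 0.145 "for main and interactive effects of all independent variables outlined above".

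On Day 2, the Study protocol says that two saliva samples "were assayed for cortisol to control for the influence of salivary cortisol levels on generalization testing". The generalization ANOVAs list stress, stress time point, sex, trial block and trial type. Day 2 cortisol appears only as the outcome of its own ANOVA.

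**The concern.** With one baseline and one later sample, the stress × time interaction is the same test as comparing mean change between arms. A change score subtracts the whole baseline value, whatever the true relation between baseline and post values. If that relation is weaker or stronger than one-for-one, the subtraction leaves avoidable noise in the comparison. Estimating the slope removes it, and randomisation ensures that the adjusted and the change analyses aim at the same stress effect.

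What is at stake is precision for the stress and stress × sex effects on Day 1 cortisol, using a sample already taken. A related matter is which term is read. The stress main effect in the planned ANOVA averages in a sample taken before the manipulation, so it estimates only half of the post-stress difference.

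**Working it through.** **The plan's own figure.** The figure of 565 cannot be reproduced from the stated inputs, because the test family, numerator df, number of measurements and correlation are not given. With f = 0.145, eight between-subjects cells (2 × 2 × 2) and a plain fixed-effects F test, 80% power needs N = 376 for 1 df, 523 for 3 df, 573 for 4 df and 690 for 7 df. The point here does not depend on 565 being reproduced.

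**Inputs.** From the documents: alpha 0.05, N = 565, power 0.8, f = 0.145, three two-level between-subjects factors. Assumed: near-equal arms, baseline SD 1, post SD k (1 to 1.5), correlation r (0.3 to 0.9).

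**Variance of the stress estimate** (per-person factor):

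- Change score: k² + 1 − 2rk
- Baseline-adjusted: k²(1 − r²)
- Example, k = 1 and r = 0.5: 0.75 / 1.00 = 0.75
- Example, k = 1.25 and r = 0.8 (rk = 1): 0.5625 / 0.5625 = 1.00, so no gain

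| Ratio, adjusted / change | r = 0.3 | 0.5 | 0.7 | 0.9 |
|---|---|---|---|---|
| k = 1 | 0.65 | 0.75 | 0.85 | 0.95 |
| k = 1.25 | 0.78 | 0.89 | 0.98 | 0.95 |
| k = 1.5 | 0.87 | 0.96 | 1.00 | 0.78 |

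**Power, anchor A: the planned test has exactly 80%.** For F(1, 557) this needs λ = 7.876. The adjusted test has λ / ratio on F(1, 556).

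| Adjusted power, A | r = 0.3 | 0.5 | 0.7 | 0.9 |
|---|---|---|---|---|
| k = 1 | 94% | 90% | 86% | 82% |
| k = 1.25 | 89% | 84% | 81% | 82% |
| k = 1.5 | 85% | 81% | 80% | 89% |

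**Power, anchor B: f = 0.145 applies to this 1-df contrast.** λ = 0.145² × 565 = 11.88, which gives the planned test 93%.

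| Adjusted power, B | r = 0.3 | 0.5 | 0.7 | 0.9 |
|---|---|---|---|---|
| k = 1 | 99% | 98% | 96% | 94% |
| k = 1.25 | 97% | 95% | 94% | 94% |
| k = 1.5 | 96% | 94% | 93% | 97% |

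The gain is therefore 0 to 14 points under A and about 0 to 6 points under B.

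**When a common slope can lose.** Take arms 2:1, post SDs 2 and 1, and r = 0.7. The pooled slope is (2/3)(1.4) + (1/3)(0.7) = 1.167. The variance is 5.325 against 5.100 for change, a ratio of 1.04. With a centred baseline × stress term it is 5.080 / 5.100 = 0.996.

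**Stress main effect.** Relative to stress × time, its λ is multiplied by (1 + k² − 2rk) / (1 + k² + 2rk). At k = 1 the factors are 0.54, 0.33 and 0.18 for r = 0.3, 0.5 and 0.7. Under anchor A its power is 54%, 37% and 22%.

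**Sex main effect.** Sex is not randomised, so adjustment and change can answer different questions. Suppose a stable sex difference of 0.3 baseline SD and no difference in change (k = 1). The adjusted model would show 0.3(1 − r) = 0.21, 0.15 and 0.09 SD at r = 0.3, 0.5 and 0.7, where the change comparison shows 0.

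**Day 2 cortisol.** Setting the two sections side by side is enough: a purpose of control is stated, and no generalization model has a cortisol term. The effect cannot be quantified from the documents.

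**The case against.** The strongest reply is that this is a preference between two legitimate methods. The plan asks about change over time, and the stress × time test answers that directly. This stands: a reader might infer that the planned test is biased or wrong, and nothing in the documents supports that.

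Second, the size is uncertain and may be negligible. A reader might take 14 points as the expected loss, but that needs r = 0.3, k = 1 and a planned test at exactly 80% power. The 565 is offered as sufficient for all main and interactive effects, not for this 1-df test. With f = 0.145 applied to this contrast, planned power is already 93%. This also stands, and the range has to include zero.

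Third, a reader might infer that the plan rests its cortisol conclusion on the stress main effect, since the power statement mentions main effects. The stated aim of change over time points to stress × time instead. What survives is only a caution on which term to read.

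Fourth, the argument does not carry over to the overall alpha-amylase test. Where the planned 2-df stress × time test has 80% power, simulations under assumed correlations put a baseline-adjusted joint 2-df test at 73% to 92% if stress acts equally on both later samples. No overall gain can be claimed.

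Finally, the Day 2 cortisol ANOVA might be all the control intended, as a check that groups are comparable. That is possible, though the text does not say so. A reader might infer that the generalization models are wrong without cortisol. They are not: Day 2 cortisol is measured after randomisation, and the second sample follows the test itself.

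**Conclusion.** The point holds as an optional efficiency improvement for Day 1 cortisol, of low severity. Adjusting for baseline is unbiased for stress and stress × sex under randomisation. In large samples with near-equal arms or similar slopes it is never less precise than the change test, and it is equal when rk = 1. The variance ratio is 0.65–0.95 at k = 1 and 0.78–1.00 at k = 1.25 to 1.5. The gain in power is 0 to 14 points from an 80% anchor, or about 0 to 6 points from 93%. All of these rest on assumed r, k and allocation, since the documents give none of them.

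The mismatch over Day 2 cortisol is real but is a matter of wording.

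**What to change.** **Day 1 cortisol.** Model the 25-minute post-stress value with the participant's own baseline as covariate and stress, stress time point and sex as factors. Take the stress and stress × sex estimates from it, and report the planned ANOVA beside it. If arms and spread are clearly unequal, add centred baseline × group terms. Keep the sex main effect with the planned ANOVA. State that the stress conclusion is read from the adjusted effect or from stress × time, not from the stress main effect. The text is in the past tense, so if the data had already been analysed, label the model post hoc.

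**Alpha-amylase.** Keep the planned 2-df stress × time test. Baseline-adjusted stress differences at each later sample are optional.

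**Day 2 cortisol.** Either reword the stated purpose of the assays, or add a labelled sensitivity analysis that uses only the pre-test Day 2 sample and notes that it is measured after randomisation. Keep the unadjusted generalization models primary.

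**Cost.** Some wording and one covariate (1 df, more if slope terms are needed), with no new data. The downside is that a second cortisol model is reported, and the sex main effect comes from a different model than stress and stress × sex.

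### The Day 2 ANOVA enters four generalization stimuli, but the protocol presents seven and gives no rule for reducing them

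*Combined protocol and SAP*

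**What the plan says.** All references are to the combined protocol and SAP.

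- **Study protocol, stimuli.** "The conditioned stimuli (CSs) and generalization stimuli (GSs) consisted of nine black circles of increasing diameter". The GSs are defined by position: "The circles sized between the CS+ and the CS- were the GSs and were only presented to participants on Day 2". The smallest circle is the CS+ for about half of participants and the largest is the CS+ for the rest.
- **Study protocol, Day 2 generalization phase.** After three initial noise-alone (NA) trials come "three blocks of one trial of each stimulus type (NA, CS+, seven GSs, CS-) for a total of 10 trials per block", 30 trials in all. The description of trial order repeats the count: "there was 1 trial of each trial type (i.e., NA, CS+, seven GSs, CS-) for each block of 10 trials".
- **Study protocol, measurement.** Skin conductance is scored for the CSs and GSs, and US expectancy is recorded on every CS and GS trial. No GS is excluded or combined with another.
- **Statistical analyses.** Startle (EMG difference scores), skin conductance and US expectancy are each analysed by mixed-model ANOVA. For Day 2 there are three blocks, and trial type is "generalization testing: CS+, CS-, 4 generalization stimuli".

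**The concern.** Day 2 exists to test generalization, and trial type is the factor that carries that question. The design section supplies seven GSs and the analysis section uses four, with nothing to link them. There are three plausible readings:

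- **(a) Subset.** Four individual circles were kept; the three left out are not named.
- **(b) Pooling.** The seven GSs were combined into four classes, whose boundaries are not given.
- **(c) Wrong digit.** Four was written for seven.

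Under (a) or (b) the choice can affect the result for all three Day 2 outcomes, and a reader cannot tell what it was or when it was made. Counterbalancing adds a second ambiguity. The CS+ is at opposite ends of the size range in the two halves of the sample, so an asymmetric subset or grouping means one thing if GSs are numbered by diameter and another if they are numbered by distance from the CS+. Under (c) nothing is lost, but the stated factor is still wrong.

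**Working it through.** **Inputs.** Nine circles; two of them CSs; one trial per stimulus type per block; three Day 2 blocks; 10 trials per block and 30 in total (Study protocol). CS+, CS- and four GSs as levels; three Day 2 blocks; alpha 0.05 with Bonferroni-adjusted post hoc tests (Statistical analyses). NA is not listed as a level of trial type, so it is left out of the level counts below.

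**1. Reproduce the design count.**
- GSs = 9 - 2 = 7.
- Trials per block = 1 NA + 1 CS+ + 7 GS + 1 CS- = 10, and 3 × 10 = 30. Both match the protocol.
- With four GSs: 1 + 1 + 4 + 1 = 7 per block, and 3 × 7 = 21. Neither matches.

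The design section is internally consistent at seven. The four in the analysis section cannot be reproduced from it.

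**2. The factor as described and as presented.** The plan gives no degrees of freedom; these follow from levels - 1. The last two rows assume that all pairs of trial types are compared post hoc, which the plan does not specify.

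| | Four GSs | Seven GSs |
|---|---|---|
| Levels | 2 + 4 = 6 | 2 + 7 = 9 |
| Trial type df | 5 | 8 |
| Trial type × block df (block df = 3 - 1 = 2) | 5 × 2 = 10 | 8 × 2 = 16 |
| All pairs | C(6,2) = 15 | C(9,2) = 36 |
| Bonferroni alpha per pair | 0.05/15 = 0.0033 | 0.05/36 = 0.0014 |

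**3. Reading (a), four circles kept.**
- CS and GS trials per participant: 9 × 3 = 27. GS trials: 7 × 3 = 21.
- Three GSs omitted: 3 × 3 = 9 trials, so 9 of 27 (or 9 of 21 GS trials) are unused.
- Possible sets of four: C(7,4) = 35. Number the GSs 1 to 7 from the CS+ end; a set is symmetric if swapping i for 8 - i leaves it unchanged. Only {1,2,6,7}, {1,3,5,7} and {2,3,5,6} qualify: 3 of 35. All three omit circle 4, the middle one.

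**4. Reading (b), all seven split into four non-overlapping classes of neighbouring circles.**
- Groupings: three cut points among six gaps, C(6,3) = 20.
- Class sizes, in some order: 2+2+2+1, 3+2+1+1 or 4+1+1+1. The largest class has 2, 3 or 4 times as many trials as the smallest.
- A symmetric grouping needs sizes a, b, b, a, whose sum 2(a + b) is even. Seven is odd, so 0 of 20 are symmetric.

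**5. Reading (c).** No trials are lost; the factor should be nine levels with 8 df.

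**6. Does the sample size settle it?** No. The plan's figure of about 565 comes with an effect size and a power, but no test family, numerator df, number of measurements or correlation, so it cannot be tied to either count. The point does not depend on it.

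**The case against.** The mismatch itself is not in dispute. The best case against making much of it has five parts.

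*A wrong digit is a live explanation.* The design gives seven repeatedly and the analysis gives four once. This stands: if it is the explanation, the remedy is one word. The document does not settle it, so the other readings cannot be excluded.

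*Four levels need not be asymmetric.* Dropping the middle circle and pooling the rest as {1}, {2,3}, {5,6}, {7} is symmetric, and so are the overlapping pools {1,2}, {3,4}, {4,5}, {6,7}. That is correct. The result in step 4 holds only for non-overlapping neighbouring classes that use all seven circles. These alternatives discard one circle or use one twice, which would equally need to be declared.

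*Numbering by distance from the CS+ is the natural reading,* because the CSs are labelled by role and nothing suggests labelling by size. This is reasonable, but the plan does not say it. The order of levels does not change the omnibus test of a categorical factor; what matters is that a given level means the same thing in both counterbalanced halves.

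*The counts are combinatorics, not a demonstrated effect on error rate, power or bias.* This stands. They measure what the text leaves open.

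*Pooling neighbours can be sensible when each GS appears once per block, and the text is in the past tense.* Both are true. Pooling is not criticised here, only its absence from the text. If the analysis has been done, the first step is to state what was done.

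**Conclusion.** The concern holds and should be fixed. By direct count, the protocol collects data on nine CS and GS trial types and the analysis plan models six, for all three Day 2 outcomes, with no rule connecting them. Confidence in that mismatch is high. Its practical size depends on which reading is true: a one-word error with no data lost, an unnamed subset that omits 9 of 27 trials per participant, or an unstated grouping with unequal classes. The all-pairs post hoc figures and the asymmetry result for pooling rest on the assumptions given with them. Nothing here is evidence that stimuli were chosen after seeing the data. The Day 1 analyses are unaffected.

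**What to change.** In the Statistical analyses section, define Day 2 trial type as nine levels: CS+, the seven GSs labelled by distance from the CS+, and CS-. Use all 27 CS and GS trials, in the same way for startle, skin conductance and US expectancy. The mixed-model ANOVA can otherwise stay as it is.

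If four levels were intended, name the exact stimuli or classes, say whether they are numbered by size or by distance from the CS+, and state when the choice was made relative to seeing the data. Report the nine-level analysis alongside, so that readers can see whether the reduction matters.

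Cost: no new participants or procedures. A wrong digit needs a one-word correction. If a six-level analysis has already been run, the three Day 2 ANOVAs need rerunning on data the protocol already collects. The trade-off is a factor with more df and, if every pair is tested, a stricter Bonferroni threshold (36 comparisons rather than 15).
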